### 2.3.2 Time Point Response

It is assumed that at each protocol specified time point, a response assessment occurs. Table 2.3.2-1 provides a summary of the overall response status calculation at each time point for patients who have measurable disease at baseline. When patients have non-measurable (therefore non-target) disease only, [Table 2.3.2-2](#) is to be used.

**Table 2.3.2-1: Time Point Response: Patients With Target (+/- Non-Target) Disease**

Target Lesions	Non-Target Lesions	New Lesions	Overall Response
CR	CR	No	CR
CR	Non-CR/non-PD	No	PR

**Table 2.3.2-1: Time Point Response: Patients With Target (+/- Non-Target) Disease**

Target Lesions	Non-Target Lesions	New Lesions	Overall Response
CR	Not evaluated	No	PR
PR	Non-PD or not all evaluated	No	PR
SD	Non-PD or not all evaluated	No	SD
Not all evaluated	Non-PD	No	NE
PD	Any	Yes or No	PD
Any	PD	Yes or No	PD
Any	Any	Yes	PD

CR = complete response, PR = partial response, SD = stable disease, PD = progressive disease and NE = inevaluable

**Table 2.3.2-2: Time Point Response: Patients with Non-target Disease Only**

Non-Target Lesions	New Lesions	Overall Response
CR	No	CR
Non-CR/non-PD	No	Non-CR/non-PD a
Not all evaluated	No	NE
Unequivocal PD	Yes or No	PD
Any	Yes	PD

CR = complete response, PD = progressive disease and NE = inevaluable

a Non-CR/non-PD is preferred over SD for non-target disease since SD is increasingly used as endpoint for assessment of efficacy in some trials so to assign this category when no lesions can be measured is not advised.

### 2.3.3 Best Overall Response

Best response determination of complete or partial response requires confirmation: Complete or partial responses may be claimed only if the criteria for each are met at a subsequent time point of  $\geq 4$  weeks later. In this circumstance, the best overall response can be interpreted as in [Table 2.3.3-1](#).

**Special note on response assessment:** When nodal disease is included in the sum of target lesions and the nodes decrease to 'normal' size ( $< 10$  mm), they may still have a measurement reported on scans. This measurement should be recorded even though the nodes are normal in order not to overstate progression should it be based on increase in size of the nodes. As noted earlier, this means that patients with CR may not have a total sum of 'zero' on the case report form (CRF).

**Table 2.3.3-1: Best Overall Response (Confirmation of CR&PR Required)**

Overall Response First Time Point	Overall Response Subsequent Time Point	BEST Overall Response
CR	CR	CR
CR	PR	SD, PD OR PR a
CR	SD	SD provided minimum criteria for SD duration b met, otherwise, PD
CR	PD	SD provided minimum criteria for SD duration b met, otherwise, PD
CR	NE	SD provided minimum criteria for SD duration b met, otherwise, NE
PR	CR	PR
PR	PR	PR
PR	SD	SD
PR	PD	SD provided minimum criteria for SD duration b met, otherwise, PD
PR	NE	SD provided minimum criteria for SD duration b met, otherwise, NE
NE	NE	NE

CR = complete response, PR = partial response, SD = stable disease, PD = progressive disease, and

NE = inevaluable

a If a CR is truly met at first time point, then any disease seen at a subsequent time point, even disease meeting PR criteria relative to baseline, makes the disease PD at that point (since disease must have reappeared after CR). Best response would depend on whether minimum duration for SD was met. However, sometimes 'CR' may be claimed when subsequent scans suggest small lesions were likely still present and in fact the patient had PR, not CR at the first time point. Under these circumstances, the original CR should be changed to PR and the best response is PR.

b Minimum criteria for SD duration is 6 weeks.

### 2.3.4 Confirmation Scans

Verification of Response: To be assigned a status of CR or PR, changes in tumor measurements must be confirmed by consecutive repeat assessments that should be performed no less than 28 days after the criteria for response are first met. For this study, the next scheduled tumor assessment can meet this requirement.

Verification of Progression: Progression of disease should be verified in cases where progression is equivocal. If repeat scans confirm PD, then progression should be declared using the date of the initial scan. If repeat scans do not confirm PD, then the subject is considered to not have progressive disease.

## LIST OF ABBREVIATIONS

IV	intravenous
IWRS	interactive web response system
LCSS	Lung Cancer Symptom Scale
LDH	lactate dehydrogenase
LLN	lower limit of normal
MedDRA	Medical Dictionary for Regulatory Activities
NCI	National Cancer Institute
NSCLC	Non-small Cell Lung Cancer
NSQ	non-squamous
PD	progressive disease
PFS	Progression-Free Survival
PK	pharmacokinetics
PPK	population pharmacokinetic
PR	partial response
PR interval	electrocardiographic interval occurring between the onset of the P wave and the QRS complex, representing time for atrial and ventricular depolarization, respectively
PRO	Patient Reported Outcomes
PS	Performance status
PT	Preferred Term
ORR	Objective Response Rate
OS	Overall Survival
Q2W	every 2 weeks
QoL	Quality of Life
QRS	electrocardiographic deflection between the beginning of the Q wave and termination of the S wave, representing the time for ventricular depolarization
QT	electrocardiographic interval between the beginning of the Q wave and termination of the T wave, representing the time for both ventricular depolarization and repolarization to occur
QTcF	QT interval corrected by Fridericia's formula
RECIST	Response Evaluation Criteria in Solid Tumors
RR	interval between successive heart beats using the R-wave peaks
SAE	serious adverse event(s)
SAP	statistical analysis plan
SAS	Statistical Analysis System software
SD	stable disease
SI	standard international unit
SOC	System Organ Class
SQ	squamous
TC	total cholesterol
TKI	tyrosine kinase inhibitor

TSH	thyroid stimulating hormone
TTF	Time to Treatment Failure
ULN	upper limit of normal
US	United States
VAS	Visual Analogue Scale
WBC	white blood cell
WHO	World Health Organization
WOCBP	women of childbearing potential

## **1 BACKGROUND AND RATIONALE**

Non-small cell lung cancer (NSCLC) second line (2L) will be launched in China in July, 2018 based on the results of the CA209-078 study, an open-label randomized multinational phase 3 trial of nivolumab versus docetaxel in previously treated participants with advanced or metastatic NSCLC. NSCLC 2L treatment in the study used weight-based dosing and will be the first indication for nivolumab in China. In CA209078 study weight based dosing with a 60 minutes infusion time was used. The study excluded patients with tumors harboring EGFR activating mutation or ALK rearrangement in order to control potential confounding OS outcomes due to subsequent use of new generation TKI. Additionally, the study used conventional eligibility criteria for phase 3 trials and limited enrollment of patients such as those with HBV infection, which is more frequently found in clinical practice in Asia. However, modeling and simulation, as well as preliminary PK data support the use of flat dose as well and a shorter 30 minute infusion time in this study. As flat based dosing will be the future nivolumab dosing for NSCLC patients and a 30 minute infusion time is more convenient for participants, this study will gather safety and efficacy data on these subjects.

The purpose of this document is to provide details about the statistical analysis methods for the study an open label, safety study of participants with non-small cell lung cancer receiving second-line nivolumab monotherapy in Asia protocol CA209870.

### **Research Hypothesis:**

There is no formal hypothesis to test in this study. The main objective of the study is to collect additional safety data on the incidence rate of high-grade select AEs and their outcomes and supplement the growing safety database of nivolumab-treated participants. This study will treat approximately 400 participants in order to estimate the incidence of the rare high grade (CTCAE V4 Grades 3-4 and Grade 5) treatment-related select AEs with greater precision and characterize their outcome. Previous studies have shown an incidence per event type between 0 to 3% in NSCLC patients treated with nivolumab monotherapy.

## **2 STUDY DESCRIPTION**

[figure not shown]
### **2.1 Study Design**

In this safety study of nivolumab monotherapy, subjects will undergo screening evaluations to determine eligibility within 28 days prior to first dose. Eligible subjects will be treated with nivolumab administered intravenously over 30 minutes at 240 mg every two weeks. Each 2 week dosing period will constitute a cycle.

Study treatment can continue beyond initial investigator assessed progression, as specified in criteria presented in Protocol. The study will close after the last enrolled subject completes 2 year follow up. Details regarding the assessments to be performed during these phases are outlined in [Appendix 1 Schedule of Activities](#).

The study design schematic is presented in [Figure 2.1](#).

**Figure 2.1: Study Design Schematic**

A Enrolled patients without EGFR mutation and ALK positive are restricted to have only 1 prior systemic therapies. Patients with EGFR mutation or ALK positive should be treated with prior 2 systemic treatment including TKI and chemotherapy. With a large percentage of NSCLC of patients with EGFR mutation (approximately 30% incidence), this population will be capped to 40 participants in the CA209870 study.

B HBsAg+ participants (estimated 15%) must be on antiviral therapy based on China anti-HBV guideline. Patients with HBV infection will be capped to 60 participants.

C Treatment until progression or unacceptable toxicity. Nivolumab treatment will be given up to 24 months in the absence of disease progression or unacceptable toxicity. Treatment with nivolumab could be reinitiated as per the initial schedule for subsequent disease progression and administered for up to 1 additional year.

D Participants may receive nivolumab treatment beyond progression as defined in protocol. The decision to continue treatment beyond initial progression should be discussed with the BMS Medical Monitor and documented in the study records.

Physical examinations, vital sign measurements, outcome questionnaires, and clinical laboratory evaluations will be performed at selected times throughout study participation. Participants will be closely monitored for AEs throughout the study. Blood samples will be collected for safety analysis.

In this study, overall survival is a key endpoint of the study. Post study follow-up is of critical importance and is essential to preserving participant safety and the integrity of the study. Participants who discontinue study drug must continue to be followed for collection of outcome and/or survival follow-up data as required until death or the conclusion of the study.

## 2.2 Treatment Assignment

All participants will be assigned to treatment using an Interactive Response Technology (IRT). Users will receive log in information and directions on how to access the IRT. Study treatment will be dispensed at the study visits as listed in Schedule of Activities ([Appendix 1](#)).

## **2.3 Blinding and Unblinding**

This is an open-label, single arm study and blinding procedures are not applicable.

## **2.4 Protocol Amendments**

Document	Date of Issue	Summary of Change
Revised Protocol 02	25-Oct-2017	Incorporates Amendment 02
Amendment 02	25-Oct-2017	Change the efficacy objective, endpoint and analyses [REDACTED] to secondary classification
Revised Protocol 01	20-Mar-2017	Incorporates Amendment 01
Amendment 01	20-Mar-2017	

• Treatment duration will have a 2-years stopping rule

• Number of EGFR mutation participants will be capped to 40 participants

• PD-L1 testing [REDACTED] will be evaluated in a central laboratory.

Original Protocol	20-Nov-2016	Not Applicable

## **2.5 Data Monitoring Committee and Other External Committees**

A Data Monitoring Committee (DMC) will not be used for this study.

## **3 OBJECTIVES**

Specific objectives relevant to the study are described within this SAP are described below.

### **3.1 Primary**

[figure not shown]
To evaluate safety and tolerability in non-HBV infected participants with advanced or metastatic NSCLC who have progressed during or after one prior systemic therapy and are treated with nivolumab monotherapy with an infusion duration of 30 min.

### **3.2 Secondary**

- To assess safety and tolerability in HBV infected participants with advanced or metastatic NSCLC who have progressed during or after one prior systemic therapy and are treated with nivolumab monotherapy with an infusion duration of 30 min
- To assess safety and tolerability in all participants
- To evaluate efficacy in participants with advanced or metastatic NSCLC who have progressed during or after one prior systemic therapy and are treated with nivolumab monotherapy

### **3.3 Exploratory**

- To assess overall health status and health utility

## **4 ENDPOINTS**

### **4.1 Primary**

Incidence and severity of high grade (combined CTCAE v4 Grade 3-4 and Grade 5) treatment-related select adverse events in non-HBV infected participants.

### **4.2 Secondary**

- Incidence and severity of all high grade (combined CTCAE v4 Grade 3-4 and Grade 5) treatment-related select adverse events in HBV participants
- Incidence and severity of AEs and specific laboratory abnormalities in all treated subjects
- Collection of overall survival (OS), time to treatment failure (TTF), progression free survival (PFS), objective response rate (ORR) , duration of tumor response (DOR) by tumor histology (SQ or NSQ), tumor PD-L1 expression level (PD-L1 negative or PD-L1 positive), by infection status (HBV infection or non-HBV infection), and by molecular type (EGFR mutation, ALK translocation, or WT).

### **4.3 Exploratory**

- The 3-level version of the EQ-5D (EQ-5D-3L) visual analog scale (VAS) and utility index, respectively
- Lung Cancer Symptoms Scale (LCSS) will use disease-related symptom deterioration rate at week 12 and week 24 and is defined as the proportion of treated subjects who had 10 points or more increase from baseline in Average Symptom Burden Index (ASBI) score at any time between first dosing and at week 12 and week 24.

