**Table 2-3: Follow-up Assessments CA209870**

Procedure	Follow-up Visits X01 (Day 35) ( $\pm$ 7 Days) and X02 (Day 100) a ( $\pm$ 7 Days) after Last Dose	Survival Follow-up Visits b Every 12 Weeks	Notes
Safety Assessments			
Targeted Physical Examination	X		
Targeted examination must include the cardiovascular, gastrointestinal, and pulmonary body systems and examination to specific malignancy
 
To assess for potential late emergent study drug related findings.

Adverse Events assessment	X		All AEs and SAEs must be collected up to 100 days after study drug discontinuation. SAEs that relate to any later protocol specified procedure must be collected.
Any subsequent cancer treatment information	X	X	
Vital signs	X		28 days from the date of last study treatment
Laboratory Tests			
Hematology and chemistry	X		
Laboratory assessments will be performed locally.
 
See Section 9.4.3

Thyroid function testing	X		TSH with free T3 and free T4
Pregnancy test	X		WOCBP only: serum or urine
Outcome Research Assessment			
LCSS and EQ-5D questionnaire	X	X	
Both LCSS and EQ-5D will occur in FU Visits 1 & 2.
 
During Survival Visits, the EQ-5D will be collected every 3 months (<math>\pm</math> 14 days) for the first year of Survival Phase, then every 6 months thereafter.
 
May be obtained through a telephone call or clinic visit.
 
See Table 9.10-1

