##### **3.1.1 *Rationale for Participant Population with NSCLC***

Substantial monotherapy clinical activity has been observed in participants with heavily pretreated advanced NSCLC in the ongoing phase 1/2 study of nivolumab (CA209003). This study showed ORR of 17% which is greater than the historical ORR for docetaxel as second line therapy for advanced NSCLC (approximately 8 to 10%). Durable responses were observed in both squamous and non-squamous subtypes. In 3 mg/kg group, ORR in squamous and non-squamous subgroups was 22% and 26% respectively and 3mg/kg group had median OS of 14.9 months. Whereas, the historical median OS for docetaxel was about 8 months. Nivolumab phase 3 second-line studies with docetaxel as comparator. CA209017 for squamous NSCLC and CA209057 for non-squamous NSCLC demonstrated significant survival benefit of nivolumab with a better safety profile in nivolumab arm compared to the docetaxel arm. Therefore, CA209870 will test the safety and efficacy of nivolumab as monotherapy in previously treated advanced or metastatic NSCLC in in Asia population.

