#### **10.3.3.1 *Patient Reported Outcomes***

The LCSS and EQ-5D completion rates, defined as the proportion of questionnaires actually received out of the expected number will be calculated and summarized at each assessment point. The EQ-5D (with two essential components: the EQ-5D descriptive system and the EQ visual analogue scale (EQ VAS) will be used to assess the subject's overall health status. Proportion of subjects reporting problems for the 5 EQ-5D dimensions at each assessment time point will be summarized by level of problem. Percentages will be based on number of subjects assessed at assessment time point. Value set for Chinese population will be used to get utility values for each individual. The baseline and change from baseline of the EQ-5D and LCSS scores at each assessment point will be summarized using descriptive statistics. The disease-related symptom deterioration rate at week 12 and week 24 as measured by LCSS and its corresponding 95% CI will also be calculated by Clopper-Pearson method. All summaries for LCSS and EQ-5D will be done for all treated participants, and also by tumor histology (SQ or NSQ), by PD-L1 expression (PD-L1 negative or PD-L1 positive), by infection status (HBV infection or non-HBV infection), and by molecular type (EGFR mutation, ALK translocation, or WT).

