### **6.3 Populations for Analyses**

The following defined population will apply to pooled tumor types and individual tumor histology and molecular genotype, unless otherwise specified:

- **Enrolled Participants:** All participants who signed an informed consent form and were registered into the IRT.
- **Treated Participants:** All enrolled participants who received at least one dose of study drug.
- **Response Evaluable Participants:** All treated participants who have baseline and at least one on-study evaluable tumor measurement.
- **Non-HBV infected participants:** All treated participants with HBVsAg negative by serum testing.
- **HBV infected participants:** All treated participants with HBVsAg positive by serum testing.
- **Biomarker participants:** All treated participants with available tissue [REDACTED] samples.

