### **7.8.2 Outcomes Research Analyses**

#### **LCSS (Lung Cancer Symptom Scale)**

The LCSS completion rates, defined as the proportion of questionnaires actually received out of the expected number will be calculated and summarized at each assessment point for all treated participants by HBV status and pooled. The baseline and change from baseline of the LCSS scores at each assessment point will be summarized using descriptive statistics.

The disease-related symptom deterioration rate at week 12 and week 24 as measured by LCSS and its corresponding 95% CI will also be calculated by Clopper-Pearson method.

All summaries for LCSS will be done for all treated participants by HBV status and pooled. In addition, subgroup analysis will be performed by tumor histology (SQ or NSQ), by PD-L1 expression (PD-L1 negative or PD-L1 positive), by infection status (HBV infection or non-HBV infection), and by molecular type (EGFR mutation, ALK translocation, or WT).

By subject listing will be provided for all treated participants.

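### The LCSS deterioration rate divides by all treated participants, so people whose symptom scores were never seen count as not deteriorated and the rate is biased low for deterioration before death

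*SAP*

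**What the plan says.** SAP 4.3, matching Protocol section 4, gives the rate this definition: "proportion of treated subjects who had 10 points or more increase from baseline in Average Symptom Burden Index (ASBI) score at any time". The count runs from the first dose to the landmark week. The treated population in SAP 6.3 is "All enrolled participants who received at least one dose of study drug"; no questionnaire is required.

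SAP 7.8.2 repeats that base: "All summaries for LCSS will be done for all treated participants by HBV status and pooled". It then plans the estimate: "The disease-related symptom deterioration rate at week 12 and week 24 as measured by LCSS and its corresponding 95% CI will also be calculated", with "its corresponding 95% CI will also be calculated by Clopper-Pearson method". The same section adds subgroup summaries by histology, PD-L1, HBV status and molecular type.

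The only LCSS missing-data rule, in SAP section 8, concerns items within a questionnaire: the symptom index is imputed if at least half its items are present and is otherwise missing. No rule covers a missing baseline index, the absence of any later index, or follow-up that stops before the landmark. Protocol 10.3 says the SAP will describe how missing data are handled.

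On collection, Protocol Table 2-3 places the LCSS at follow-up visits 1 and 2, about 35 and 100 days after the last dose. For later contacts its note names only the other instrument: "During Survival Visits, the EQ-5D will be collected every 3 months".

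**The concern.** The numerator needs an observed rise of at least 10 points; the denominator needs only one dose. Anyone whose rise could not be observed stays in the denominator and cannot reach the numerator. This is what the definition produces, not a rule the SAP writes out.

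Three groups are affected:

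- participants without a usable baseline index;
- participants without any post-baseline index;
- participants who stop treatment early, whose scheduled LCSS collection ends before week 24, unless a rise was recorded first.

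The exact interval treats these unknown outcomes as known negatives, so it is narrow around the wrong value. The protocol synopsis wants patient-reported data to support policy decisions. A rate that falls as more scores go missing is a weak basis for that.

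**Working it through.** **The plan's interval method.** The documents give no expected LCSS rate, so there is no stated LCSS figure to reproduce. The nearest check is SAP Table 5.1, which uses the same interval. Exact Clopper-Pearson limits with 2, 4 and 12 events of 400, and 2, 4 and 11 events of 340, reproduce all six intervals to two decimals.

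**Effect of missing scores alone.** Let p be the rate among participants with usable scores and m the share of treated participants without them. The planned rate is p × (1 − m). Assume p = 30%, m = 20%, N = 400:

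- usable: 400 × 0.80 = 320; deteriorated: 0.30 × 320 = 96
- planned: 96/400 = 24.0% (95% CI 19.9 to 28.5)
- among those with usable scores: 96/320 = 30.0% (25.0 to 35.3)

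Over p = 20% to 40% and m = 5% to 30%, the planned rate is 1.0 to 12.0 points lower (0.20 × 0.05 to 0.40 × 0.30).

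**When collection stops.** Follow-up visit 2 is about 100 days after the last dose, and week 24 is day 168. Since 168 − 100 = 68, a participant whose last dose came before about day 68 (week 10) has no scheduled LCSS up to week 24. Week 12 is day 84, which is less than 100, so scheduled collection passes week 12 for everyone. Early stopping of collection is therefore a week-24 problem.

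**Early death.** Protocol 3.1.1 says the "3mg/kg group had median OS of 14.9 months". With exponential survival (assumption) and 30.4375 days per month:

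- week 12 (2.76 months): 1 − 2^(−2.76/14.9) = 12%
- week 24 (5.52 months): 1 − 2^(−5.52/14.9) = 23%

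At the 8-month docetaxel median in the same section, the figures are 21% and 38%.

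**Benchmark: true deterioration before death by week 24, among all treated.** Assume 30% would deteriorate by week 24 if nobody died.

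- cumulative hazard of deterioration: −ln(0.70) = 0.357
- cumulative hazard of death: ln 2 × 5.52/14.9 = 0.257
- true rate: 0.357/0.614 × (1 − e^(−0.614)) = 0.581 × 0.459 = 26.7%

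Deaths are already in this denominator.

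**What the plan would report at week 24.** Simulation with these hazards, LCSS every 4 weeks on treatment and at 35 and 100 days after the last dose, and median treatment of 2 to 4 months (assumption):

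| Estimate at week 24 | Result |
|---|---|
| True deterioration before death | 26.7% |
| Planned rate, complete baselines | 21.5% to 23.0% |
| Planned rate, 10% missing baselines (× 0.90) | 19.4% to 20.7% |
| Baseline plus at least one later score as denominator | 22.6% to 24.1% |
| Cumulative incidence, censored at last LCSS, death competing | about 25% |

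The last two rows assume complete baselines. The planned-rate shortfall is 3.7 to 5.2 points with complete baselines (26.7 − 23.0; 26.7 − 21.5) and 6.0 to 7.3 points with 10% missing (26.7 − 20.7; 26.7 − 19.4). Other reasonable layouts of the visit days put the complete-baseline rate at 22.3% to 23.6%. About 25% to 43% of simulated participants were still alive when their LCSS collection ended before week 24. That lost follow-up and the wide spacing of post-treatment visits cause most of the shortfall when baselines are complete. Restricting the denominator recovers only about 1.1 points.

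**The case against.** The strongest objection concerns deaths. A reader might infer that everyone who dies without a recorded rise is wrongly scored, and that deterioration or death is the figure the plan hides. The documents do not support that. The endpoint is a symptom rise, and the plan nowhere defines a composite with death. If death is a competing event, the dead belong in the denominator, as they do in the 26.7% benchmark. This objection stands, and deaths are not part of the bias claimed here.

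A reader might also see a contradiction with the EQ-5D, where "Percentages will be based on number of subjects assessed at assessment time point" (Protocol 10.3.3.1). That rule covers dimension levels at a single visit, while the LCSS rate accumulates over time. The two quantities may properly have different denominators, and all treated is also the base for ORR. This objection stands too.

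Nor do the documents show that missing LCSS scores come mainly from progression or toxicity, or that subgroups with faster attrition would look better; such subgroups may also deteriorate more.

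Finally, the SAP reports LCSS completion and change from baseline at each assessment, and OS separately. A careful reader can therefore see that data are missing. That limits the harm but does not correct the rate, because nothing links completion to it. The baseline questionnaire is mandatory before the first dose, so 10% missing may be pessimistic. Table mock-ups are in a Data Presentation Plan that is not available here and might already show evaluable counts.

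**Conclusion.** The concern holds as a minor point. For deterioration before death, unobserved outcomes enter the planned rate as negatives, so the rate and its interval are biased low. The direction follows from the definition, apart from measurement noise around the 10-point threshold.

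The size is not fixed by the documents. The deterioration rate, treatment duration and share of missing baselines are assumptions, and the 14.9-month median comes from an earlier study in heavily pretreated patients. The simulation also takes a rise to last until the next questionnaire. On those inputs the week-24 shortfall is about 4 to 5 points with complete baselines and 6 to 7 with 10% missing. At week 12 scheduled collection covers everyone, so only missing or uncompleted questionnaires and visit spacing matter.

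The week-24 size also takes LCSS collection to end at follow-up visit 2, as the Table 2-3 note indicates. The combined LCSS and EQ-5D row does carry a mark under survival visits; if the LCSS were collected there, the loss would be smaller.

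No sample size, power or error rate is affected. The endpoint is exploratory, in a single-arm study with no formal hypothesis.

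**What to change.** In SAP 7.8.2:

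1. Add the cumulative incidence of a first ASBI rise of 10 points or more at weeks 12 and 24, among treated participants with a baseline ASBI. Censor at the last LCSS assessment, and treat death during LCSS follow-up as a competing event.
2. Keep the protocol-defined all-treated proportion, labelled as observed deterioration.
3. Beside it, overall and by subgroup, show the numbers with no baseline score, with no post-baseline score, and dead by each landmark.

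Do not make the evaluable-only denominator the main estimate. Someone with one week-4 score who then drops out would still count as not deteriorated, and the restriction conditions on surviving to a questionnaire.

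The cumulative incidence is not a complete cure. It assumes that participants censored after stopping treatment deteriorate at the same rate as those still followed, and it misses rises between the last questionnaire and death. In the simulation it reaches about 25%, against 26.7%.

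The cost is a little extra programming on data already collected, and a somewhat less favourable reported rate.
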